11.1.3. Definition of Serious Adverse Event

SAE, as per FDA regulations defined in 21 CFR 312.32(a), is considered “serious” if, in the view of either the Investigator or Sponsor, it results in any of the following outcomes: death, a life-threatening adverse event, in-patient hospitalization or prolongation of existing hospitalization, a persistent or significant /incapacity or substantial disruption of the ability to conduct normal life functions, or a congenital anomaly/birth defect. Important medical events that may or may not result in death, be life-threatening, or require hospitalization may be considered a serious adverse drug experience when, based upon appropriate medical judgment, they may jeopardize the subject and may require medical or surgical intervention to prevent one of the outcomes listed in this definition.

If either the Sponsor or Investigator believes that the event is serious, the event must be considered serious and evaluated by the Sponsor for expedited reporting (21 CFR 312.32(a) and 312.32(c) (1)).

11.1.4. Definition of Treatment Emergent Adverse Event of Special Interest

The TEAEs of special interest (TEAESI) will be selected based on the list of appropriate MedDRA terms provided by the Sponsor. The TEAESI will include the following items: Gastrointestinal (nausea, vomiting and diarrhea), Hematologic Impairment-Related adverse events. The full list will be provided before the study is unblinded. The lists of terms (PTs) will be located in Appendices ().

11.2. Summaries of Adverse Event

All adverse event verbatim text will be coded and classified by system organ class (SOC) and preferred term (PT) using the MedDRA (Version 20.1). AE summary tables will use the following algorithms for counting subject events within the summary tables:

- Preferred term rows: Each subject is counted once within each unique preferred term at the maximum grade. Subjects experiencing the same AE preferred term several times with different grades would only be counted once with the maximum grade.
- System organ class rows: Each subject is counted only once in the maximum grade at each system organ class level, although they may have several different preferred term events within the same SOC.
- Any event row: Each subject with an event is counted only once at the maximum grade although they may have several events. For drug related AE table, each subject with an event is counted only once at the most related although they may have several events.

Unless specified otherwise, the summaries of adverse events will be based on the safety population.

TEAEs will be presented in alphabetical order of System Organ Class and within each System Organ Class, in decreasing order of the total number of combined TAS-102 patients who experienced each TEAE at the preferred term level.

11.2.1. Overview and Summaries of Adverse Events

AE incidence will be calculated by the worst CTCAE grade at every level of summarization (SOC or PT), i.e., if a patient has multiple occurrences of the same AE with different toxicity grades during a period, the patient will be accounted for in AE frequency tabulation in the worst grade. An overall summary table (overview) of all adverse events will be presented, summarizing:

- Total number of TEAE
- Total number of Serious TEAE
- Total number of TEAESI
- Total number and percentage of subjects with at least one TEAE
- Total number and percentage of subjects with at least one Serious TEAE
- Total number and percentage of subjects with at least one related TEAE
- Total number and percentage of subjects with at least one related Serious TEAE
- Total number and percentage of subjects with at least one severe (Grades 3 - 5) TEAE
- Total number and percentage of subjects with at least one TEAE leading to dose modification
- Total number and percentage of subjects with at least one TEAE leading to dose reduction
- Total number and percentage of subjects with at least one TEAE leading to discontinuation of the study treatment
- Total number and percentage of subjects with at least one TEAE leading to death
- Total number and percentage of subjects with at least one TEAESI

The primary AE summary will also be all TEAE by SOC and PT regard to the relationship to study medication (AT population CCI).

In addition to the overview table, a number of the summaries will be created. The primary AE summary will tabulate all TEAE by SOC and PT (AT population CCI - Section 4.1). Other summaries will present various aspects of collected AE. Calculations in the tables will follow the basic principles of counting described in the beginning of Section 11.2. The following summaries will be created:

- TEAE (all and grades 3-5) summarized by SOC and PT, by treatment group (AT population CCI)
- TEAEs (all and grades 3-5) related to study drug summarized by SOC and PT, by treatment group (AT population CCI)
- TEAE summarized by SOC and PT, by CTCAE grades, by treatment group (AT population)
- TEAE (all and grades 3-5) summarized by PT in descending order, by treatment group (AT population)
- TEAE (all and grades 3-5) related to study drug summarized by PT in descending order, by treatment group (AT population)
- TEAE (all and grades 3-5) leading to dose modification summarized by SOC and PT, by treatment group (AT population)

- TEAE (all and grades 3-5) leading to dose reduction summarized by SOC and PT, by treatment group (AT population)
- TEAE (all and grades 3-5) leading to treatment discontinuation summarized by SOC and PT, by treatment group (AT population)
- TEAE (all and grades 3-5) leading to death summarized by SOC and PT, by treatment group (AT population)
- TEAE of Special Interest (all and grades 3-5) summarized by SOC and PT, by treatment group (AT population CCI [REDACTED])
- Incidence rate (per 100 patient years) of all TEAESIs (summarizing the incidence rate (per patient year) for each SOC and PT as per description in [Section 8.9.](#))
- Serious TEAE (all and grades 3-5) summarized by SOC and PT, by treatment group (AT population CCI [REDACTED])
- Serious TEAE (all and grades 3-5) related to study drug summarized by SOC and PT, by treatment group (AT population CCI [REDACTED])
- Serious non-treatment emergent AE (all and grades 3-5) summarized by SOC and PT, by treatment group (AT population)
- Selected adverse events and lab abnormalities of special interest (the exact list will be determined prior to study unblinding) will be presented in the graphical form (“forest plot” format). Figure will include the relative risk and associated 95% asymptotic confidence intervals

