13.3.2.3. Secondary Endpoint Analyses

All secondary endpoints comparisons will be made at the 2-sided 0.05 significance level. Since PFS is the only key secondary endpoint for regulatory registration purposes, no further multiplicity adjustments will be made. Assuming that OS demonstrates significance at the 1-sided 0.025 level, PFS can subsequently be tested at the 2-sided 0.05 level.

PFS

PFS will be analyzed with the methodology specified in Section 13.3.2.1 and Section 13.3.2.2a, c, and d. CCI

ORR and DCR

The treatment comparison for ORR and DCR will be based on the TR population using Fisher's exact test. Treatment estimates and differences will be presented along with the associated 95% CIs.

Time to Deterioration of ECOG Performance Status

Time to deterioration of ECOG performance status to a score of 2 or higher will be analyzed using methodology described in Section 13.3.2.1. Patients not reaching an ECOG of 2 or more (3, 4 or 5) will be censored at the last recorded ECOG assessment.

Quality of Life

Questionnaire compliance rates, for both scales, will be assessed at each measurement time point (baseline, prior to cycle 2, 3, 4, etc.).

Descriptive statistics, for both scales, for the summary scores, as well as the subscale scores will be provided for each assessed time point. In addition, change in QoL scores at representative time points will be determined for the summary, all domains and single items by subtracting each patient's score from their corresponding baseline score. Representative time points will be prior to cycle 2, 3 and 4, chosen based on expected patient compliance to be adequate to allow meaningful analyses, considering the expected treatment duration in the two study groups.

For each domain, the proportion of patients with deteriorating, stable or improving scores prior to cycles 2, 3 and 4 will be compared using Fisher's exact test. In addition, time to QoL deterioration will be evaluated for each arm using Kaplan-Meier estimates and compared using the log-rank test. The criteria for deteriorating, stable or improving scores will be detailed in the SAP.

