4.3. Sample Size Considerations

4.3.1. Sample Size Justifications

The study is designed to detect with 90% power a hazard ratio for death of 0.70 (30% risk reduction) in the TAS-102 arm compared with the placebo arm with an overall 1-sided type 1 error of 0.025. A variable accrual period of 18 months and a 5%/year loss to survival follow-up rate has been assumed. Using a treatment allocation of 2:1 (TAS-102:placebo) of 500 patients, 384 deaths will be targeted for the final OS analysis.

Based on these design operating characteristics and assuming a median survival time of approximately 5 months in the control arm, the primary analysis target events milestone will be reached approximately 8 months after the last patient is randomized in the study. The median OS in the control arm was estimated based on the observed median OS of 3.8 months in the placebo arm of the 2nd line Phase 3 ramucirumab (REGARD) study, and the observed median OS of 4.3 months in the placebo arm of the 2nd & 3rd line Phase 3 everolimus (GRANITE) study [13]. The estimate was further increased to 5 months to account for the higher control median projected in the Japanese population.

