11.1.2. Definition of Treatment Emergent Adverse Event

Treatment-emergent adverse events (TEAE) will be defined as those events, which meet one of the two criteria:

- started on or after treatment start date (first dose of study medication ⇔ Cycle1, Day 1) through 30 days after treatment end date (last dose of study medication)
- started before treatment start date and became worse (more severe) after treatment start date (first dose of study medication ⇔ Cycle1, Day 1) through 30 days after treatment end date (last dose of study medication)

Only treatment-emergent adverse events will be summarized, non-treatment emergent AE will be listed only.

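### Serious, Grade 3-5, discontinuation and fatal TEAEs are planned only as crude percentages over a window that lengthens with time on treatment; exposure-adjusted rates should stand beside them

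*SAP*

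**What the plan says.** SAP 11.1.2 counts a TEAE from the first dose "through 30 days after treatment end date (last dose of study medication"). Protocol 8.5 and 8.5.1 fix no treatment length: patients continue until a stopping criterion is met, and RECIST-defined and clinical progression are both on that list.

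SAP 8.9 defines an incidence rate per 100 patient-years for any event or TEAE. In the legible text two outputs use it:

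- SAP 11.2.1: "Incidence rate (per 100 patient years) of all TEAESIs". SAP 11.1.4 limits that set to "Gastrointestinal (nausea, vomiting and diarrhea), Hematologic Impairment-Related adverse events".
- SAP 11.6.1: Grade 3 or 4 abnormalities in haemoglobin, neutrophils and platelets, with Poisson 95% intervals.

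The headline categories in SAP 11.2.1 are counts and percentages of subjects, for example "Total number and percentage of subjects with at least one Serious TEAE". The Grade 3-5, treatment-discontinuation and fatal rows have the same form. For selected adverse events and laboratory abnormalities of special interest there is also a forest plot: "Figure will include the relative risk and associated 95% asymptotic confidence intervals". Its list of items is still to be fixed before unblinding.

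The only mention of treatment duration in both groups is in Protocol 13.3.2.3, which picks the quality-of-life time points "considering the expected treatment duration in the two study groups". It gives no figure.

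**The concern.** The window is time on treatment plus 30 days. A drug that delays progression keeps its patients on treatment, and so under observation for harms, for longer. Where events accrue steadily, the longer-treated arm collects more of them even if its event rate is no higher, and equal crude percentages could hide a lower rate. If toxicity shortened TAS-102 treatment instead, the distortion would run the other way and crude figures would understate harm on TAS-102.

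The SAP has a tool for this and applies it to the expected gastrointestinal and haematologic toxicities, but not to the categories most likely to be read as the overall harm comparison. Safety and tolerability is listed with PFS as key secondary (Protocol 7). Safety must support a favourable benefit/risk ratio before open-label TAS-102 is offered (Protocol 8.2 and 9.3), and the SAP is meant to support a marketing application (SAP 3).

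**Working it through.** **The plan's own figure.** The documents give no power or rate figure for the safety comparison. The nearest design figure is 90% power for OS (SAP 4.3.1). With 384 deaths, HR 0.70, 2:1 allocation and one-sided 0.025: √(384 × 2/9) × |ln 0.70| − 1.96 = 9.24 × 0.357 − 1.96 = 1.33, which is 90.9% power. It reproduces, and nothing below affects it.

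**Inputs**

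- Window: treatment time plus 30 days, w = 30/30.44 = 0.99 months (SAP 11.1.2).
- TAS-102 time on treatment: exponential, median 2.9 months. Assumption, set equal to the phase 2 median PFS in Protocol 6.1.2.2. Mean m = 2.9/0.693 = 4.18 months.
- Ratio k of placebo to TAS-102 treatment time: assumption, 0.50 to 0.85. The middle value 0.70 borrows the OS design hazard ratio.
- Event rate L = 0.10 per month in both arms: assumption, so the true rate ratio is 1.

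**Case A: constant hazard.** Mean window = k·m + w. Crude incidence = 1 − exp(−wL)/(1 + L·k·m). For TAS-102 (k = 1) this is 1 − 0.906/1.418 = 36.1%, with a mean window of 5.17 months.

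| k | Placebo window (months) | Shortfall | Placebo crude incidence | Crude RR |
|---|---|---|---|---|
| 0.85 | 4.54 | 12% | 1 − 0.906/1.356 = 33.2% | 1.09 |
| 0.70 | 3.91 | 24% | 1 − 0.906/1.293 = 29.9% | 1.21 |
| 0.50 | 3.08 | 40% | 1 − 0.906/1.209 = 25.1% | 1.44 |

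Expected person-time to first event or end of window is incidence/L, so the 8.9 rate returns L in each arm and a ratio of 1.00 in every row. At k = 0.70, the same formula gives a crude RR of 1.25 with L = 0.05 and 1.15 with L = 0.20. A TAS-102 median of 2.0 months at k = 0.70 and L = 0.10 gives a 22% shortfall and a crude RR of 1.21.

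**Case B: early events.** With the hazard confined to the first 2 months, the crude RR is only 1.02 (k = 0.70) to 1.05 (k = 0.50). The rate ratio falls below 1, because the longer-treated arm adds person-time in which no events occur.

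**Case C: events tied to the end of treatment.** Let each patient have the same probability p of an event when treatment stops. The crude RR is p/p = 1.00 for any k. Person-time per patient is k·m + (1 − p)w, so the TAS-102:placebo rate ratio is [k·m + (1 − p)w]/[m + (1 − p)w]. With p = 0.25 (assumption):

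- k = 0.70: (2.93 + 0.74)/(4.18 + 0.74) = 0.75
- k = 0.50: (2.09 + 0.74)/(4.18 + 0.74) = 0.58

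Per-patient risk is identical, yet the rate appears to favour TAS-102. This case is realistic: Protocol 12.1.3 and 12.1.4 require signs, symptoms and complications of progression to be reported as AEs or SAEs, and progression is a reason to stop treatment.

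**The case against.** Three stronger readings are tempting, and the documents support none of them.

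*The trial expects treatment duration to differ by arm.* A reader might infer this from the quality-of-life sentence in Protocol 13.3.2.3. That sentence concerns questionnaire compliance and does not say that the arms differ. A difference is a reasonable inference from treatment to progression and the hoped-for benefit, but its size and direction are assumptions.

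*The crude comparison is biased against TAS-102, so the between-arm statement should rest on rates.* The crude percentage is a valid description of risk during treatment plus 30 days. It misleads about event intensity only if exposure differs and events accrue over time. In Cases B and C the crude RR is right or nearly so, and the rate ratio is the misleading measure, in the drug's favour. Replacing one with the other would exchange one possible error for another.

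*The forest plot would often raise a false alarm.* Under Case A at k = 0.70, with 333 v 167 patients, a 95% interval for the relative risk would lie wholly above 1 with probability 27% rather than 2.5%. However, the SAP plans that interval only for selected items of special interest. It plans none in the legible text for the serious, Grade 3-5, discontinuation or fatal categories, and the special-interest TEAEs and three laboratory tests already have companion rates.

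Other points also stand. Cycles initiated and cycle duration are tabulated by arm (SAP 9.7), so unequal exposure will be visible. The SAP contents list has a redacted entry between 11.2.1 and 11.2.3, so further adjusted outputs cannot be ruled out. Section 8.9 also needs tightening: it ends time at risk at last dose plus 30 days for patients without an event and does not mention death or new antitumour therapy, although Protocol 12.1.1 stops AE collection when new therapy starts.

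These arguments limit the size of the point and rule out rates as the sole basis. They do not remove the gap in the headline categories.

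**Conclusion.** The point holds in a limited form. In the legible SAP, the four headline categories have no exposure-adjusted summary, although their window depends on time on treatment and the derivation already exists. Under a roughly constant hazard and the assumed durations, the crude RR would be 1.09 to 1.44 with equal true rates. For early or end-of-treatment events the distortion is close to nil, and the rate ratio errs in favour of the longer-treated arm. Neither measure can be read safely alone, so both should be planned before unblinding. No primary-endpoint, alpha or sample-size figure is affected. This is an inexpensive improvement to the safety reporting and does not show that the planned tables are wrong.

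**What to change.** In SAP 11.2.1, for serious, Grade 3-5, discontinuation and fatal TEAEs, add the 8.9 rate per 100 patient-years with a Poisson 95% CI and the TAS-102:placebo rate ratio, beside and not instead of the crude percentages. In the forest plot, show the rate ratio beside the relative risk.

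In SAP 8.9, end time at risk at the earliest of first event, death, start of new antitumour therapy, data cut-off, or last dose plus 30 days.

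State that both measures are interpreted together and that the between-arm statement does not rest on rates alone. For the fatal and discontinuation rows, cumulative incidence with competing events is an alternative.

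Cost: about one more table and a short revision of 8.9; the basic derivation is already specified. Downside: the rate assumes a roughly constant hazard, which is why the crude percentages must stay.

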11.2.3. Missing and Partial AE Onset Dates

The start/onset dates for AEs are important for the:

1. Treatment emergent algorithm.
2. Designation of unique AE occurrences.

Completely missing or partially missing AE onset dates will be queried and every reasonable effort will be made to resolve the issue and to obtain accurate AE information from site, investigator or any other trustful source. Once all attempts of this kind has failed, the missing or partially missing AE onset date will be imputed.

The following algorithm should be used to impute adverse event start dates for which only partial information is available.

1. If onset date is completely missing or the year of the end date is missing:
 - a. Set onset date to the date of the first treatment if the end date of the AE (if available) remains sensible after imputation (i.e., imputed start date precedes end date).
 - b. Set onset date to the 1st of January of the same year as the end date is if the end date of the AE (if available) presumes that the AE ended before the first treatment of the study.
2. If (year is present and month and day are missing) or (year and day are present and month is missing):
 - a. If year = year of the first dose, then set month and day to month and day of first dose.
 - b. If year \neq year of the first dose, then set month and day to January 1st.
3. If month and year are present and day is missing:
 - a. If year and month = year and month of first dose, then set month and day to month and day of first dose.
 - b. If year and month \neq year and month of first dose, then impute the first day of the available month.

Imputed dates will be flagged in the individual supportive subject listings.

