8.13.2. Missing Start and Stop Dates for Prior and Concomitant Medication

Incomplete concomitant medication start and/or stop dates will be imputed as follows. If either the start of medication date is completely missing or the month and/or year of the start date is missing, the start date will be set to the first dose date. If only the day is missing, the day will be set to the first day of the month except if the start month is the same as the first dose month. If the latter is true, the start day will be set to the first dose day. No imputations will be applied to the stop date. Imputed dates will be flagged in the individual supportive subject data listings.

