8.13.3. Missing Start and Stop Dates for Adverse Events

No imputation for stop dates of TEAEs will be performed.

Missing and/or partial start dates of TEAEs will be imputed using the algorithms presented in the

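### Step 1 of the AE onset-date imputation tests the year of the end date instead of the onset date, so some partial dates meet two conflicting steps and others meet none

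*SAP*

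**What the plan says.** SAP 11.2.3 sets out an algorithm to "impute adverse event start dates for which only partial information is available", used after queries to the site have failed.

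- **Step 1** applies in this case: "If onset date is completely missing or the year of the end date is missing". Under 1a the instruction is "Set onset date to the date of the first treatment if the end date of the AE (if available) remains sensible after imputation". Under 1b, if the end date shows that the event finished before first treatment, onset becomes 1 January of the end-date year.
- **Step 2** applies when the onset year is known but the month is not. It gives the first-dose month and day if the year is the first-dose year, otherwise 1 January.
- **Step 3** applies in this case: "If month and year are present and day is missing". It gives the first-dose date if the month and year match first dose, otherwise the first of the known month.

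The section states no order of precedence beyond the numbering. SAP 8.13.3 adds: "No imputation for stop dates of TEAEs will be performed". The parallel rule for medications in SAP 8.13.2 is triggered differently: "If either the start of medication date is completely missing or the month and/or year of the start date is missing".

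**The concern.** The algorithm imputes an onset date, yet step 1 branches on the end date. An ongoing event has no end date and none is imputed, so its end year is always missing. If its onset is partial it therefore meets step 1, even when the onset month and year are known and step 3 would place it in that month. In the other direction, steps 2 and 3 both need a known onset year. The case of an unknown onset year, which step 1 would be expected to catch, is caught only if the onset is wholly missing or the end year also happens to be missing.

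SAP 11.2.3 itself says that onset dates serve two purposes: treatment-emergent status and the designation of unique occurrences. Onset also sets time at risk in SAP 8.9, which feeds the rates per 100 patient-years for events of special interest in SAP 11.2.1. Two programmers following the text could derive different dates for the same record.

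**Working it through.** The plan gives no figure to reproduce, so the check is a logical enumeration.

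**Inputs.** The triggers of steps 1 to 3 (SAP 11.2.3); no imputation of stop dates (SAP 8.13.3); complete onset dates are outside the algorithm.

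**Patterns.** Year, month and day of onset can each be known or missing, which gives 2 × 2 × 2 = 8 patterns. Removing the complete date leaves 7. Crossing these with end year known or missing gives 7 × 2 = 14.

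| Known part of onset | As written, end year known | As written, end year missing | Step 1 keyed to onset year (either end-year state) |
|---|---|---|---|
| nothing | 1 | 1 | 1 |
| day only | none | 1 | 1 |
| month only | none | 1 | 1 |
| month and day | none | 1 | 1 |
| year only | 2 | 1 and 2 | 2 |
| year and day | 2 | 1 and 2 | 2 |
| year and month | 3 | 1 and 3 | 3 |

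As written there are 3 gaps and 3 overlaps. With the trigger keyed to the onset year there are 0 and 0.

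**Illustration**, assuming a first dose on 20 January 2016:

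- Ongoing event, onset March 2016, day unknown. Step 1a gives 20 January 2016; step 3 gives 1 March 2016. The difference is 11 + 29 + 1 = 41 days.
- Ongoing event, onset 2017, month and day unknown. Step 1a gives 20 January 2016; step 2 gives 1 January 2017.
- Ongoing event, onset December 2015, day unknown. Step 1a gives 20 January 2016, which is treatment-emergent; step 3 gives 1 December 2015, which is before treatment.
- Event that ended in 2016, onset 5 March, year unknown. No step applies.

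The two answers agree only when the onset month is the first-dose month, or when the month is unknown and the year is the first-dose year.

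**Effect on a rate.** SAP 8.9 defines time at risk as (first onset − drug start + 1)/365.25. If the March 2016 event is that patient's first of its kind, step 3 gives (41 + 1)/365.25 = 0.115 patient-years and step 1a gives (0 + 1)/365.25 = 0.003. The patient still counts once in the numerator, so the step 1a date shrinks the denominator and raises the rate.

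**Evidence that the trigger is a slip.** Step 1b uses the end-date year, which cannot be evaluated in a branch entered because that year is missing. The medication rule in SAP 8.13.2 tests the start date. Changing the trigger to the onset year makes the three steps fit together exactly.

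**The case against.** The strongest reply is that the intended meaning can be recovered from the text, and that little depends on it.

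- *No precedence is stated.* A reader might infer that ongoing events with partial onsets are definitely moved to first dose. The text does not establish that: it happens only if the steps run in numbered order and the first match wins. A programmer could equally treat steps 2 and 3 as the more specific rules. This objection stands; what the text contains is a conflict.
- *Treatment-emergent status.* A reader might infer that pre-treatment and late events would often become treatment-emergent. The documents narrow this. Events between consent and first dose go to Medical History (Protocol 10.1.3 and 10.1.15; SAP 11.1.1). Events after the follow-up window count only if judged related to study drug (Protocol 10.1.15 and 12.1.1). A pre-existing event that worsens on treatment is treatment-emergent in any case (SAP 11.1.2). Such reclassification is possible but should be uncommon.
- *Main AE tables.* These count each patient once at maximum grade (SAP 11.2), so moving an onset within the treatment window does not change them. The hematology rates in SAP 11.6.1 concern laboratory results. Both points stand.
- *Few records.* Queries come first, imputed dates are flagged, and complete onsets are untouched. A known onset day and month with no year is unlikely to survive querying. This stands.
- *Redaction.* SAP 8.13.3 breaks off where it names the location of the algorithms, and SAP 14 mentions a Data Handling Guidance appendix with further safety rules. It therefore cannot be said that the whole SAP lacks a rule for the uncovered patterns, only that 11.2.3 as published does.

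None of this makes the step 1 trigger correct.

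**Conclusion.** Step 1 of SAP 11.2.3 is wrong as written, and the point is minor. The published section gives two competing dates for 3 of 14 patterns and no date for another 3. The result rests on reading 11.2.3 alone; the redacted appendix might settle the conflict.

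The size cannot be stated as a number, because the documents do not say how many onset dates remain partial after query. For each affected record the discrepancy depends on how far the true onset lies from first dose; the 41 days above are an illustration on an assumed first-dose date. The consequences are confined to time at risk in the special-interest event rates and the designation of unique occurrences, with an occasional change in treatment-emergent status. Overall survival, progression-free survival and the other efficacy analyses do not use these dates.

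**What to change.** In the step 1 trigger, change the second condition so that it tests the year of the onset date instead of the year of the end date. That one-word substitution alone makes every partial-date pattern meet exactly one step, so no precedence sentence is needed. Check that the Data Handling Guidance and the derivation program use the same trigger. Because imputed dates are flagged, the affected records can be counted from the listings. The cost is one word in the SAP and a short check of the program; no data collection, sample size or efficacy analysis changes.
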